7.3 Labelling

A numbering system will be used to label the blinded IP. A list linking the label number with the product lot number will be maintained by the groups (or companies) responsible for study drug packaging. In order to maintain the blind, the list will not be accessible to individuals involved in study conduct.

7.4 Storage

The investigational product must be stored refrigerated at 2-8°C (36-46°F) and must not be frozen. The investigational product will be allowed to warm to room temperature prior to administration. Due to COVID-19, drug may be shipped to local providers using cold transport shipping or courier. Local providers will confirm IP is stored at 2-8°C (36-46°F) until the IP is administered. To minimize storage risks, the investigational product will be shipped to local providers 1-2 days prior to the patient's planned local injection.

7.5 Compliance

Drug compliance records must be kept current and must be available for inspection by the sponsor and regulatory authorities.

7.6 Accountability

Drug accountability records must be kept current at all times. The investigator must be able to account for all opened and unopened study drug. Records should contain the following:

Dates, quantity, and study medication

- dispensed to each patient (if applicable) including drug shipped to local provider for patients that cannot travel to the study site due to COVID-19
- returned from each patient (if applicable), and
- disposed of at the site or returned to the manufacturer or designee.

Accountability records must be available for inspection by the AstraZeneca and regulatory authorities. Photocopies must be provided to the sponsor at the conclusion of the study.

Prohibited Medication/Class of drug:	Washout Period Prior to Study Screening (i.e. Study Entry)
Anti-immunoglobulin E [IgE] mAb	6 months
Anti-tumor necrosis factor [TNF] mAb)	6 months
Other investigative biologic	6 months
Anti-IL 5 agents	6 months
Anti-IL 4/13 agents including anti-IL4Ra	6 months
Other investigative drugs or device	1 month

7.7 Concomitant and other treatments

Rescue/Supportive Medication/Class of drug:	Usage:
Study participants should continue their baseline medications and dietary therapy. Rescue medicines for EGID exacerbations are not allowed and will lead to study withdrawal.	
During study visits, participants will be allowed to have EMLA or topical analgesic (Pain Ease or Spray & Stretch) for the purpose of venepuncture/IV insertion	

7.7.1 Other concomitant treatment

Throughout the study duration, all participants are expected to maintain medications such as a PPI, oral or nasal allergy medications (such as antihistamines and any asthma-related medications) as well as special diets including elimination diets that were prescribed prior to study entry.

8. STATISTICAL ANALYSES

8.1 Statistical considerations

Pertaining to the primary objective of this study, the primary efficacy endpoint is the eosinophil count response rate to the treatments. The comparison of response rates between the benralizumab and placebo groups will be made with a Fisher's exact test of binomial distributions. For secondary endpoints, continuous variables comparisons between the two groups, e.g. change in peak eos counts, change in blood eosinophil count, change in symptom scores from pre- to post-treatment, and change in endoscopic scores from pre- to post-treatment at each study visit (e.g. Weeks 4, 8 and the end of treatment) will be made in a repeated measure ANOVA model, where serial correlation within patients will be accounted for. Proper transformation of data, e.g. logarithmic, or non-parametric methods may be applied to satisfy statistical assumptions. Categorical responses, e.g. response rate will also be compared using a Fisher's exact test, by visit if applicable. Additional exploratory analysis to investigate other

factors' effect on response may also be performed, with generalized linear models with appropriate link functions.

All comparisons are two-sided, and p-value < 0.05 is considered statistically significant. No multiplicity adjustment will be made for this analysis.

Safety measurements, including adverse events will be summarized by descriptive statistics. The total numbers of AE's as well as number of patients with an AE will be summarized via N and percent.

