To assess changes in histologic features before and after treatment with benralizumab	Change in histologic score from pre- to post-treatment with benralizumab or placebo as measured by HSS for EoE and EG and ED Biopsy Evaluation Forms for EG or EGE
To assess changes in blood eosinophil counts before and after treatment with benralizumab	Change in blood eosinophil count before and after treatment with benralizumab or placebo as measured by CBC with differential.
To assess changes in clinical symptoms before and after treatment with benralizumab	Change in symptoms from pre- to post-treatment with benralizumab or placebo as measured by PROs -SODA (for EG) -PEESSv2, PedsQL 3.0, EESAI, EoE-QOL-A, PROMIS (for EoE)
To evaluate esophageal, gastric, and duodenal tissue transcriptome changes following benralizumab treatment.	Baseline predictors and changes in expression of genes as assessed by whole genome RNA sequencing
To assess changes in peak eosinophil counts in biopsies before and after treatment with benralizumab	Change in peak eosinophil count in biopsies (esophageal, gastric, and/or duodenal, as applicable) pre- vs. post-treatment with benralizumab or placebo

Safety Objective:	Outcome Measure :
To evaluate the safety and tolerability of	AEs/SAEs
Benralizumab in subjects with EG	Vital signs
	Physical exam
	Collection of blood chemistry and hematology
	Urinalysis
	Pregnancy testing

Target subject population

Male and female subjects between the ages of 12-60 with histologically active EG.

Duration of study

3 months during the double blind treatment and up to 20 months during the open label extensions. Due to COVID-19, some participants may remain in the study up to an additional 3 months.

Investigational product, dosage and mode of administration

Benralizumab 30 mg or placebo Subcuteaneous injection

Statistical methods

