2.2 Secondary objectives

Secondary Objective:	Outcome Measure :						
To assess changes in endoscopic score before and after treatment with benralizumab	Change in endoscopic score from pre- to post- treatment with benralizumab or placebo as measure by EREFS for EoE and Lanza Score for EG						
To assess changes in histologic features before and after treatment with benralizumab	Change in histologic score from pre- to post- treatment with benralizumab or placebo as measured by HSS for EoE and EG and ED Biopsy Evaluation Form for EGE						
To assess changes in blood eosinophil counts before and after treatment with benralizumab	Change in blood eosinophil count before and after treatment as measured by CBC						

To assess changes in clinical symptoms before and after treatment with benralizumab	Change in symptoms from pre- to post-treatment with benralizumab or placebo as measured by PROs -PEESSv2, PedsQL 3.0, EESAI, EoE-QOL-A (for EoE) -SODA (for EG) -PROMIS
To evaluate esophageal, gastric, and duodenal tissue transcriptome changes following benralizumab treatment.	Baseline predictive transcripts and changes in expression of genes as assessed by whole genome RNA sequencing
Comparison between peak eosinophil counts before and after drug or placebo	Change in histological features including peak eosinophil count in biopsies (esophageal, gastric, and/or duodenal, as applicable) pre- vs. post- treatment with benralizumab or placebo

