4. STUDY PLAN AND TIMING OF PROCEDURES

Study Procedures	Screening	Doul	ole-Blind Treat	ment				OLE			
	V1	V2 Baseline	V3	V4†	V5 EOT/EW OLE 1st dose	V6 OLE 2 nd dose	V7 OLE 3 rd dose	V8 (phone call)	V9†† OLE 4 th dose	V10 (phone call)	V11 EOT/EW (***1 st dose OLEII
Week (Wk)	Wk -8 to 0	WK 0	4	8	12	16	20	24	28	32	36
Visit Window (in days, d)⁺	±4 d	±4 d	±4 d	±4 d	±4 d	±4 d	±4 d	±4 d	±4 d	±4 d	±4 d
EoE-QOL-A ²	х	х	х	х	х	X**	х	х	х	х	х
SODA ³	Х	х	х	х	х	X**	х	х	х	х	х
EREFS ⁴	Х				х						х
PEESSv2 ⁵	Х	Х	Х	х	Х	X**	Х	х	х	х	х
PedsQL 3.0 ⁶	Х	Х	Х	х	Х	X**	Х	х	х	х	х
PROMIS ⁷	Х	Х	Х	х	Х	X**	Х	Х	х	х	х
Lanza Score	Х				Х						х
Histology Assessments ⁸	Х				Х						х
Safety:	-	-	-								
Weight	Х	Х	х	х	х	Х	х		х		х
Vital signs	Х	х	х	х	х	х	х		х		х
Physical Exam	Х				х	Х*					х
Adverse events	Х	х	х	х	х	х	х	х	х	х	х
Laboratory Testing:											
Hematology and serum chemistry	Х		х		х						х
CBC with Differential					X**	X**	х		х		х
HBsAG	Х										
Hepatitis C Ab	Х										
lgE	Х				х						х
Urinalysis	Х		х		х		х		х		х
Pregnancy testing - Serum	Х										
Pregnancy testing - Urine	х	х	х	Х	х	Х	х		х		х

Study Procedures	Screening	Doul	ole-Blind Treat	ment	OLE								
	V1	V2 Baseline	V3	V4†	V5 EOT/EW OLE 1st dose	V6 OLE 2 nd dose	V7 OLE 3 rd dose	V8 (phone call)	V9†† OLE 4 th dose	V10 (phone call)	V11 EOT/EW (***1 st dose OLEII		
Week (Wk)	Wk -8 to 0	WK 0	4	8	12	16	20	24	28	32	36		
Visit Window (in days, d)⁺	±4 d	±4 d	±4 d	±4 d	±4 d	±4 d	±4 d	±4 d	±4 d	±4 d	±4 d		
Endoscopy with biopsies ⁹	х				х						х		
Research samples (whole blood/serum)	Х	Х	х	х	Х	х	х		Х		Х		
Tissue transcriptome (esophagus, stomach, and duodenum)	х				х						х		
Stool microbiome	х				х						Х		

¹EESAI = eosinophilic esophagitis symptom activity index; ²EoE-QOL-A = Adult Esophagitis Quality of Life Questionnaire; ³SODA = severity of dyspepsia assessment; ⁴EREFS = endoscopic reference score; EOT = end of treatment; EW = early withdrawal ⁵PEESS = Pediatric EoE Symptom Score; ⁶PedsQL = Pediatric Quality of Life; ⁷PROMIS = Patient Reported Outcomes Measurement System; ⁸HSS for esophageal biopsies; EG Biopsy Evaluation form for gastric biopsies; ED Biopsy Evaluation form for duodenal biopsies. ⁹SOC qualifying Endoscopy will be a part of screening. EOT of unscheduled endoscopies will be covered by the study.

² Study drug administration and related activities= every 4 or 8 weeks, determined ad-lib by the study doctor depending upon symptoms and COVID-19 restrictions

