8.4 Outcome measures for analyses

The primary efficacy endpoints are the eosinophil count response rate to the treatments. A disease remission is defined by peak eosinophil counts less than 15 for esophagus, less than 30 for stomach, and less than 52 for duodenum. A patient is considered in remission if all applicable counts are in remission range. The rate of remission among all patients is the primary efficacy measure for both treatment groups.

Secondary outcome measures include individual disease remission rate, changes in endoscopic scores from pre to post-treatment as measured by EREFS for EoE and Lanza score for EGE, changes in histologic scores from pre to post-treatment, changes in blood eosinophil count pre and post-treatment, changes in symptom scores from pre to post-treatment measured by EESAI, EoE-QoL-A (for EoE), and SODA (for EGE), and changes in peak eosinophil counts in biospies from pre to post-treatment.

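### The secondary RNA-sequencing outcome has no analysis of its own, and the plan's only significance rule, unadjusted p<0.05, would leave false positives uncontrolled if applied gene by gene

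*Combined protocol and SAP*

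**What the plan says.** Section 2.2 lists a secondary objective, "To evaluate esophageal, gastric, and duodenal tissue transcriptome changes following benralizumab treatment", with the outcome measure "Baseline predictive transcripts and changes in expression of genes as assessed by whole genome RNA sequencing". The synopsis gives nearly the same outcome: "Baseline predictors and changes in expression of genes as assessed by whole genome RNA sequencing". That makes two questions (expression change and baseline prediction) in three tissues. The study plan tables in section 4 schedule tissue transcriptome samples at visits 1, 5, 11 and 24. Visits 1 and 5 bracket the double-blind period.

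Section 8.1 describes Fisher's exact test for response rates and repeated-measures ANOVA for continuous secondary endpoints. The clinical scores it names are examples, not a closed list. It also allows exploratory generalized linear models for factors that affect response. It then sets one rule: "All comparisons are two-sided, and p-value < 0.05 is considered statistically significant. No multiplicity adjustment will be made for this analysis".

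Nothing in section 8 names the transcriptome:
- The list in 8.4 opens with "Secondary outcome measures include individual disease remission rate, changes in endoscopic scores from pre to post-treatment", continues through histologic scores, blood eosinophils, symptom scores and peak counts, and ends there.
- Section 8.5.2 repeats the methods of 8.1.
- Section 8.5.6 allows further analysis of exploratory objectives, but section 2 lists none.
- Section 5.7, on biomarkers, deals with storage, shipment, custody and consent for samples.

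No false discovery rate, gene filter, fold-change threshold or validation step appears anywhere.

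**The concern.** An unadjusted 0.05 level is tolerable for a handful of clinical scores, where a reader can see how many tests were done and weigh each one. It does not serve as a criterion for thousands of genes in three tissues, because the number of false declarations grows in proportion to the number of genes tested.

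Gene-expression change is a continuous secondary outcome, so on a plain reading the rule for all comparisons covers it. The plan also goes further than silence: it rules adjustment out, so an analyst who applied false discovery control would be departing from the written text. At stake is whether a published list of drug-responsive or predictive genes carries any known error rate. The primary remission comparison is not at stake.

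**Working it through.** **Inputs from the documents.** Three tissues and two questions (section 2.2); two-sided 0.05 with no adjustment (section 8.1); 12 completers per arm (section 8.2).

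**The plan's own figure.** Section 8.2 gives 12 per arm for 80% power at 10% v 70% with a two-sided Fisher's exact test. Exact enumeration gives 75.5% at 11 per arm and 82.6% at 12, so the figure reproduces. It concerns remission only; the plan states no figure for the transcriptome.

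**Inputs that must be assumed.** The number of genes tested, *m*; the share truly affected, *π*; and the per-gene power.

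**Step 1: false positives.** Expected number = 0.05 × *m* × (1 − *π*), per tissue and per question. The ceiling, at *π* = 0, is:
- *m* = 10,000: 500
- *m* = 20,000: 1,000 (3,000 over three tissues, for each question)
- *m* = 60,000: 3,000

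**Step 2: per-gene power.** For a two-sample t comparison at 0.05 with 12 per arm, power is 22% at a standardized difference d = 0.5, 47% at 0.8, 65% at 1.0, 80% at 1.2 and 94% at 1.5. An assumed 80% power therefore needs d of about 1.2, which is generous for moderate effects.

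**Step 3: false share of the declared list.** Share = 0.05(1 − *π*) / [0.05(1 − *π*) + power × *π*]; *m* cancels. Counts at *m* = 20,000 and 80% power:

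| Share affected | True declared | False declared | False share |
|---|---|---|---|
| 2.5% (500 genes) | 400 | 975 | 975/1,375 = 71% |
| 5% (1,000) | 800 | 950 | 950/1,750 = 54% |
| 10% (2,000) | 1,600 | 900 | 900/2,500 = 36% |
| 20% (4,000) | 3,200 | 800 | 800/4,000 = 20% |

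As power runs from 100% down to 20%, the false share is 49–83% with 5% affected, 31–69% with 10% and 17–50% with 20%.

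**Step 4: break-even.** False genes are the majority when *π* < 0.05/(0.05 + power). At 80% power that is 0.05/0.85 = 5.9%; at 20% power it is 0.05/0.25 = 20%.

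**Step 5: effect of false discovery control.** Take *m* = 20,000, 5% affected and d = 1.5.
- Unadjusted: true 1,000 × 0.94 = about 940; false 19,000 × 0.05 = 950.
- Cutoff at which the expected false share is 5%, about p < 0.0015: per-gene power is 53%, so about 530 true genes and about 28 false (28/558 = 5%).

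**The case against.** The strongest reply is that the plan never prescribes gene-by-gene testing at p<0.05. The rule follows text on remission, eosinophil counts, symptoms and endoscopy, and refers to a single analysis. Section 8 contains no transcriptome model, contrast or test. This stands in part: a reader might infer that the plan commits the sponsor to a p<0.05 gene list, and the documents do not say so. The omission from 8.4 does not settle the matter either way, since that list also leaves out PROMIS, PEESS and PedsQL, which section 2.2 includes. But if the rule does not reach the transcriptome, a secondary objective has neither a method nor an error rate. Both readings call for a written rule.

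A reader might also infer that the list is bound to be dominated by false positives. The documents do not support that, because they give neither the gene count nor the share affected. Above about 5.9% affected at 80% power, true genes are the majority. Nor is a complete absence of effect a fair base case for the drug v placebo question: section 1.1 says the drug depletes eosinophils in tissue, so some change in expression is to be expected. It is a more natural worry for baseline prediction, and for segments without disease, since section 3.1 allows but does not require involvement beyond the stomach.

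Finally, it would go too far to say that the objective cannot be answered. The sequencing data are unaffected by the rule, and false discovery control can be computed later from the same p-values.

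**Conclusion.** The concern holds in this form: a named secondary outcome has no analysis of its own, and the only rule that could apply to it leaves genome-wide error uncontrolled. Per tissue and per question, the rule allows up to about 500 to 3,000 false positives for an assumed 10,000 to 60,000 features. The false share runs from about 71% to 20% as the share affected rises from 2.5% to 20%, at an assumed 80% per-gene power; lower power makes it worse. A mostly false list is possible, and most plausible for baseline prediction and uninvolved tissue, but it is not established. The change should be made, though it does not touch the primary test, the sample size or the clinical secondary endpoints.

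**What to change.** In sections 8.1 and 8.5.2, exempt the transcriptome outcome from the unadjusted p<0.05 rule. State that genes are declared by Benjamini-Hochberg false discovery rate, for example at 5%, separately within each tissue and each question (drug v placebo change; baseline prediction), and that unadjusted gene-level p-values are descriptive only. The 5% level and the per-tissue scope are conventional choices that the documents do not dictate; what matters is fixing them before the data are analyzed. The same text should name the gene filter, model and contrast, because the error rate is defined only once the set of tests is. Leave the rule for the clinical endpoints as it is.

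The cost is a few sentences of analysis text, with no new patients or samples. The real downside is lost discoveries: in the example in step 5, true detections fall from about 940 to about 530, in exchange for false ones falling from about 950 to about 28.

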8.2 Sample size estimate

The planned total sample size of 24 subjects is justified based on previously published studies. Based on trials of other therapies in EoE and EGID, it is reasonable to assume that an eosinophil count at or below 15, 30 and 52 eos/hpf in esophagus, stomach and duodenum, respectively, after treatment, is considered an adequate response. It is estimated that in the placebo group, the response rate will be no more than 10%. We assume that the benralizumab group response rate will be about 70%. To detect a difference between these two response rates, we need a total of 24 completed subjects, or 12 subjects per arm to reach 80% statistical power. This is based on a two-sided Fisher's exact test at 0.05 level. We will enroll 26 subjects to account for possible dropouts.

8.3 Definitions of analysis sets

8.3.1 Efficacy analysis set

There will be one efficacy analysis set. That is the intention-to-treat (ITT) set. This comprises all enrolled patients who took at least one dose of study medication.

8.3.2 Safety analysis set

Safety analysis set comprises all patients enrolled in the study.

8.3.3 PK analysis set

N/A

8.3.4 PRO analysis set

PRO analysis sets are the same as Efficacy analysis sets.

8.4 Outcome measures for analyses

The primary efficacy endpoints are the eosinophil count response rate to the treatments. A disease remission is defined by peak eosinophil counts less than 15 for esophagus, less than 30 for stomach, and less than 52 for duodenum. A patient is considered in remission if all applicable counts are in remission range. The rate of remission among all patients is the primary efficacy measure for both treatment groups.

Secondary outcome measures include individual disease remission rate, changes in endoscopic scores from pre to post-treatment as measured by EREFS for EoE and Lanza score for EGE, changes in histologic scores from pre to post-treatment, changes in blood eosinophil count pre and post-treatment, changes in symptom scores from pre to post-treatment measured by EESAI, EoE-QoL-A (for EoE), and SODA (for EGE), and changes in peak eosinophil counts in biospies from pre to post-treatment.

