The planned total sample size of 24 subjects is justified based on previously published studies. Based on trials of other therapies in EoE, it is reasonable to assume that an eosinophil count at or below 30 eos/hpf for the stomach is considered an adequate response. It is estimated that a response rate in the placebo group will be no more than 10%. The estimated benralizumab response rate is 70%. To detect a difference between these two response rates, we need a total of 24 completed patients, or 12 patients per arm, to reach 80% statistical power. To account for possible dropouts, we will enrol at least 26 patients. At the end of OLE, we will use descriptive statistics to analyze the OLE data including histology, eosinophil counts, PROs etc.

SUMMARY OF CHANGES

Page no.	Sections	Change description
17	1.3 Study design	Due to COVID-19 travel restrictions, investigational
27	4. Study plan	product injections and some safety procedures may occur
33	4.2 Treatment period	for double blind and open label visits at the patient's local
35	4.4 OLE I	provider. Local providers may administer injections at
37	4.5 OLE II	visits 4,6,7,9 and 12-23 per PI discretion. Safety procedures that may occur at local provider or local lab include urine pregnancy test, urinalysis, vitals, and CBC with differential per PI discretion
		When IP administration and safety procedures occur at local providers, lab results and date/time of injection and other records will be provided to study staff post visit.
25	3.8 Post injection monitoring	Post injection monitoring will occur at local providers who are medically trained to perform this monitoring including monitoring for hypersensitivity reactions. Study staff will confirm that local providers have standard treatments for hypersensitivity reactions in stock. Reactions related to injections will be logged by local providers.
50	7.4 Storage of IP	Local providers who receive and store IP for local administration will confirm IP storage temperatures for study staff. To minimize risk and monitoring burden, IP will be shipped 1-2 days before injection.
50	7.6 Accountability	Date and quantity of IP dispensed for shipment to local providers will be maintained in drug accountability records. Local providers will provide study staff with date/time of IP injection.

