2. STUDY OBJECTIVES

2.1 **Primary objective**

Primary Objective:	Outcome Measure:
To assess the efficacy of repeat subcutaneous (SC) doses of benralizumab, compared with placebo, to reduce eosinophilic inflammation in the gastrointestinal tract of patients with EG.	Induction of disease remission defined by the percentage of patients that achieve histological remission in the stomach as defined by peak eosinophil counts less than 30/hpf. Comparison between drug vs placebo will be the primary measurement endpoint.

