3. SUBJECT SELECTION, ENROLLMENT, RANDOMIZATION, RESTRICTIONS, DISCONTINUATION AND WITHDRAWAL

3.1 Inclusion criteria

Informed Consent: Able to give written informed consent prior to participation in the study, which will include the ability to comply with the requirements and restrictions listed in the consent form. Subjects must be able to read, comprehend, and write at a level sufficient to complete study related materials.

Males and females between the ages of 12-60 years

Confirmed diagnosis of EG involving stomach; involvement of eosinophilic inflammation in other gastrointestinal segments will be allowed but not required or sufficient.

Histologically active EG at time of screening, with a peak Gastric count of \geq 30 eos/hpf in at least 5 hpfs.

Must be symptomatic (defined as having experienced symptoms within 4 weeks prior to enrollment). Clinical symptoms (i.e., abdominal pain, bloating, vomiting, diarrhea) must be severe enough to impact daily life (e.g., school/work attendance, social activities) ≥ 2 times in 3 of the 4 weeks prior to enrollment despite treatment (such as diet, proton pump inhibitors or corticosteroids). See addendum number 1, page 59.

Blood eosinophilia (defined as having an absolute eosinophil count > 0.5 K/ mcL of blood) at least once during the 6 months prior to enrollment.

Must be on baseline anti-EG/EGE therapy as long as there is agreement to not change their dosage unless medically indicated; OR, must have failed anti-EG/EGE therapy in the past, including diet therapy.

Female subjects: Women of childbearing potential (WOCBP) must use an effective form of birth control (confirmed by the Investigator). Effective forms of birth control include: true sexual abstinence, a vasectomized sexual partner,

Implanon, female sterilization by tubal occlusion, any effective IUD intrauterine device/IUS levonogestrel Intrauterine system, Depo-Provera(tm) injections, oral contraceptive, and Evra Patch(tm) or Nuvaring(tm). WOCBP must agree to use effective method of birth control, as defined above, from enrollment, throughout the study duration and within 16 weeks after last dose of IP, and have negative serum pregnancy test result on Visit 0.

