8.5 Methods for statistical analyses

8.5.1 Analysis of the primary variable(s)

The comparison of primary response/remission rates between the benralizumab and placebo groups will be made with a Fisher's exact test of binomial distributions.

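### Two different primary endpoints are named, gastric remission and remission at all applicable sites; no rule says which governs, and one sample-size calculation serves both

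*Combined protocol and SAP*

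**What the plan says.** All references are to the combined protocol and SAP.

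- **Synopsis and 2.1.** The primary outcome is the percentage of patients who "achieve histological remission in the stomach as defined by peak eosinophil counts less than 30/hpf", and the drug-placebo comparison of that percentage is named as the primary endpoint.
- **8.4.** Remission needs a peak count below 15 in the esophagus, below 30 in the stomach and below 52 in the duodenum, and "A patient is considered in remission if all applicable counts are in remission range". The resulting rate is called the primary efficacy measure. The next paragraph begins: "Secondary outcome measures include individual disease remission rate".
- **8.1 and 8.5.1.** These specify Fisher's exact test but not the site. Section 8.1 says "the primary efficacy endpoint is the eosinophil count response rate to the treatments"; 8.5.1 refers to "The comparison of primary response/remission rates between the benralizumab and placebo groups".
- **Synopsis, Statistical methods.** The basis for the sample size is that "an eosinophil count at or below 30 eos/hpf for the stomach is considered an adequate response", with 70% versus 10%, 12 per arm and 80% power.
- **8.2.** The same rates, number and power follow from a different basis: "an eosinophil count at or below 15, 30 and 52 eos/hpf in esophagus, stomach and duodenum, respectively, after treatment, is considered an adequate response".
- **3.1.** Every patient must have active gastric disease at screening; elsewhere, "involvement of eosinophilic inflammation in other gastrointestinal segments will be allowed but not required or sufficient".

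**The concern.** This is the trial's only primary comparison, and the current text permits two primary results that can disagree. On the natural reading, gastric remission is primary in 2.1 and secondary in 8.4. An analyst who follows 8.4 and one who follows 2.1 are both following the protocol. Section 8.1 makes no multiplicity adjustment, so a choice made after the data are seen would leave the type I error of the primary claim uncontrolled.

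The disagreement is not confined to rare cases. Section 1.1 reports preliminary evidence that most patients with EG also have esophageal disease, so a second site may count for many of those enrolled. Section 8.4 also does not define which sites are applicable. Section 1.2.2 has all three sites biopsied, which would allow every biopsied site to count; 3.1 points instead to sites with disease at entry.

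**Working it through.** **1. Reproduce the plan's figure.** Inputs from 8.2: 70% versus 10%, two-sided Fisher's exact test at 0.05, 12 per arm. Exact power sums over all outcomes (a responders on drug, b on placebo):

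Power = Σₐ Σ_b Bin(a; n, p₁) · Bin(b; n, p₀) · 1{Fisher p(a, b) < 0.05}

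This gives 75.5% at 11 per arm, **82.6% at 12** and 88.0% at 13 (26 enrolled, none lost). Twelve per arm is the smallest size that reaches 80%, so the arithmetic behind 24 is sound.

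**2. Relation between the endpoints.** Every patient has gastric disease at entry (3.1), so the stomach is always an applicable site. All-site remission is therefore a subset of gastric remission, and in each arm its rate is equal or lower.

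**3. Power for the endpoint that 70%/10% does not describe.** The documents give no second set of rates. Every pair below is an assumption, evaluated with the same formula at 12 per arm.

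| If 70%/10% describes | Assumed rates for the other endpoint | Power |
|---|---|---|
| Gastric (synopsis) | all-site 50% v 7% | 52% |
| | all-site 61% v 9% | 69% |
| | all-site 65% v 5% | 86% |
| | all-site 60% v 0% | 94% |
| All-site (8.2 read with 8.4) | gastric 70% v 20% | 61% |
| | gastric 75% v 20% | 72% |
| | gastric 80% v 20% | 81% |
| | gastric 80% v 10% | 95% |

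Power can move either way, depending on which arm's rate changes more.

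**4. How few patients change the result.** Expected gastric responders are 0.70 × 12 = 8.4 and 0.10 × 12 = 1.2, so take 8 v 1. With equal arms, the two-sided Fisher p is twice the upper hypergeometric tail.

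- 8 v 1: 2 × [C(12,8)·C(12,1) + C(12,9)] / C(24,9) = 2 × (5,940 + 220) / 1,307,504 = **0.009**
- 7 v 1: 2 × (9,504 + 495) / 735,471 = **0.027**
- 6 v 1: 2 × (11,088 + 792) / 346,104 = **0.069**
- 6 v 0: 2 × 924 / 134,596 = **0.014**
- 4 v 0: 2 × 495 / 10,626 = **0.093**

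Starting from 8 v 1 on the gastric endpoint, two drug-arm patients who fail only at another site (6 v 1) remove significance. If the single placebo responder also fails elsewhere (6 v 0), significance is kept. The counts are illustrative.

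**5. Boundary.** Both sample-size texts count a value equal to the cut-off as a response; both endpoint definitions exclude it. This affects only a patient whose peak count equals the cut-off exactly.

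**The case against.** The documents lean towards the stomach. It is the primary outcome in the synopsis and in 2.1, the synopsis sample size is gastric, and eligibility rests on gastric disease, so 8.4 could be read as the outlier. That makes the likely resolution plain, but it does not supply one: 8.4 is the section on outcome measures for analysis, it explicitly labels its measure primary, and no section is given precedence.

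The most natural meaning of *applicable* is a segment with disease, since 2.2 uses the word in a similar way and the instruments are paired with diseases. A site already below its cut-off at entry would matter only if it crossed the cut-off by end of treatment. This point stands, so the missing definition is a secondary matter.

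Section 8.2 lists three thresholds without saying that all must be met; the all-sites rule comes only from 8.4. The lower half of the power table depends on reading the two sections together.

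Finally, the power figures have no settled direction. The documents give no rate of discordance between sites, and section 1.1 speaks to how common esophageal disease is, not to how often it fails to remit when the stomach does. Close agreement in the drug arm is possible. This also stands: the figures show that the choice can matter, not that power is lost. The difference between *at or below* and *less than* is editorial.

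**Conclusion.** The concern holds and must be fixed. Current operative sections name two different primary endpoints with no rule between them. That conclusion rests on the text alone and needs no assumption about rates. The 24-patient calculation is correct for one endpoint with 70% versus 10% (82.6% power), and the plan ties it to two. Power for the other endpoint is not stated and cannot be verified from the documents; the assumed pairs shown span 52% to 95%. The endpoints coincide only if, in every patient whose stomach remits, all other applicable sites do too.

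**What to change.** Before unblinding:

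1. State one primary endpoint in identical words in the synopsis, 2.1, 8.1, 8.2, 8.4 and 8.5.1. Gastric peak count below 30/hpf at the end-of-treatment EGD is the natural choice, because it is the stated primary outcome and every patient has gastric disease at entry. The all-site endpoint would also remove the contradiction if the synopsis and 2.1 were changed to match.
2. Keep the other endpoint as a named secondary.
3. Define the applicable sites, for example those at or above their remission cut-off on the screening biopsy. Settle the boundary when doing so: 1.1 requires more than 52 for duodenal disease, so a count of exactly 52 needs an explicit rule.
4. Attach 70%/10% and the 80% power statement to the chosen endpoint only. If that is the all-site endpoint, justify the rates for it.
5. Use *less than* in both sample-size texts, to match the endpoint definitions.

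The cost is a wording amendment, which under 10.5 needs IRB approval before implementation. It needs no additional procedures. It needs no additional patients if 70%/10% is retained for the chosen endpoint.
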